9.4.10 Biomarkers

The change from baseline in the serum/plasma biomarkers repulsive guidance molecule a (RGMa), neurofilament light (NFL), micro RNA miR-146a and miR-338, mRNAs for PLP1 (proteolipid protein 1), glial fibrillary acidic protein (GFAP), and BDNF (brain-derived neurotrophic factor), will be summarized using an MMRM. The model will include the fixed effects of treatment, visit, the stratification factors of diagnosis of MS (RRMS or rSPMS) and background MS immunotherapy (Yes or No), and the treatment-by-visit interaction, with baseline value for the respective parameter as a covariate. The REPEATED statement will be used for visit with blocks in the covariance matrix identified by subject nested within treatment group. The unstructured covariance structure will be used to estimate the within subject variance-covariance.

9.4.11 MRI Parameters

The MRI parameters of interest and analyses are listed in Section [4.3.3](#).

The number and percentage of subjects with active lesions will be summarized for T1 GAD-enhancing lesions and T2 hyperintense lesions (separately). The difference in the proportion between elezanumab and placebo groups with the 95% confidence interval for the difference based on Wald confidence limits will be presented.

The cumulative number of total T1 GAD-enhancing lesions, cumulative number of total T2 hyperintense lesions, cumulative number of post-baseline T1 GAD-enhancing lesions, cumulative number of post-baseline new and enlarging T2-lesions, will be summarized with continuously and analyzed using an analysis of covariance (ANCOVA). The model for the analysis of the cumulative number of total lesions will include treatment, the stratification factors of diagnosis of MS (RRMS or rSPMS) and background MS immunotherapy (Yes or No). For the cumulative number of lesions during the treatment period, only subjects with Baseline, Week 24, and Week 52 MRIs will be included. For the cumulative number of lesions post-baseline, only subjects with Week 24 and Week 52 will be included.

The number of T1 GAD-enhancing lesions at each visit (Baseline, Week 24, Week 52) will be summarized categorically with the number and percent of subjects for the following categories: 0, 1, 2, 3, 4, 5, > 5.

The following endpoints will be analyzed using change or percent change from baseline using an ANCOVA model.

- Change from Baseline in total volumes of T1 GAD-enhancing lesions
- Change from Baseline in total volume of T2 hyperintense lesions
- Percent change from Baseline in whole brain, gray matter (GM), thalamus, white matter (WM) and normal appearing white matter (NAWM) volumes
- Change from Baseline in regional magnetization transfer ratio (MTR) parameters for whole brain, and NAWM, and MTR for T2 lesions

- Change from Baseline in diffusion tensor imaging (DTI) parameters (fractional anisotropy and Apparent Diffusion Coefficient (ADC)) for whole brain, NAWM and T2 hyperintense lesions
- Change from Baseline in cervical spinal cord area, volume and number of lesions
- Change from Baseline in regional MTR for cervical spinal cord lesions
- Change from baseline in DTI parameters (fractional anisotropy and ADC) for cervical spinal cord

The model for the change from baseline analysis will include treatment, the stratification factors of diagnosis of MS (RRMS or rSPMS) and background MS immunotherapy (Yes or No), and the baseline value. For each treatment group, the number of subjects, mean, standard deviation, minimum, and maximum, will be presented, as well as the LS means and standard error, and the between group difference, standard error, and 95% confidence interval.

The change from baseline in lesion MTR for T1 GAD-enhancing lesions and delta MTR will be analyzed using an MMRM. The change from baseline will be calculated for each unique lesion within a treatment group. A dummy code will be created based on each subject-lesion to describe each unique lesion. The model will include the fixed effects of treatment, visit, the stratification factors of diagnosis of MS (RRMS or rSPMS) and background MS immunotherapy (Yes or No), and the treatment-by-visit interaction, with baseline MTR value as a covariate. The RANDOM statement will be used for each subject. The REPEATED statement will be used for visit with blocks in the covariance matrix identified by unique lesion nested within subject nested within treatment group. The unstructured covariance structure will be used to estimate the within subject variance-covariance. If the model fails to converge, the first order autoregressive (AR[1]) covariance structure will be substituted. If the model still fails to converge, the compound symmetry (CS) covariance structure will be substituted. Denominator degrees of freedom will be computed using the Kenward-Roger method.

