3.7 Exploratory Endpoints

- 1. Disability improvement response rate on the T25FW, 9HPT, either hand, and EDSS at Weeks 12, 24, 36, and 52, and the EDSS + at Weeks 12, 24, and 36.
- 2. Change from Baseline on the T25FW and 9HPT, either hand, at Weeks 12, 24, 36, and 52
- 3. Disability progression response rate on the EDSS+ (T25FW, 9HPT, either hand, EDSS) and for each EDSS + component
- 4. 12- and 24-week confirmed disability improvement response rate on the EDSS + (T25FW, 9HPT, either hand, EDSS) and for each EDSS + component
- 5. Change from Baseline on the MS Impact Scale (MSIS-29) version 2 at Weeks 12, 24, 36, and 52
- 6. Change from Baseline on the Modified Fatigue Impact Scale (MFIS) at Weeks 12, 24, 36, and 52
- 7. Change from Baseline on cognition battery at Weeks 12, 24, 36, and 52:
 - Symbol Digit Modalities Test (SDMT) Oral Version
 - Brief Assessment of Cognition Verbal Memory Immediate Recall BAC App Version

- Brief Assessment of Cognition Tower of London BAC App Version
- Change from Baseline on the Low Contrast Visual Acuity (LCVA) assessments at Weeks 12, 24, 36, and 52
- 9. Change from Baseline in plasma biomarkers at Weeks 12, 24, 36, and 52
- 10. Change from Baseline on the MS Individualized Outcome Assessment (Multiple Sclerosis Individualized Outcome Assessment [MSIOA]) scale at Weeks 24 and 52
- 11. Change from Baseline in one week average daily step count and other activity measures (via home actigraphy with wearable biosensor) initiated at Weeks 24, 36, and 52

MRI Endpoints

The following imaging tests will be conducted. Details will be provided in the Statistical Analysis Plan (SAP).

- Lesion counts and volumes
- Brain and spinal cord atrophy measures
- Magnetization transfer ratio (MTR)
- Diffusion tensor imaging (DTI)

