APPENDIX E. PROTOCOL SUMMARY OF CHANGES

Previous Protocol Versions

Protocol	Date
Version 1.0	30 August 2018
Version 2.0	01 February 2019
Version 3.0	07 August 2019
Version 4.0	25 November 2020

Protocol Summary of Changes

The purpose of this version is the removal of on-site assessments performed at Weeks 64 and 76 so that all visits in the Follow-up period can be conducted virtually. Other administrative revisions were made throughout the protocol, including the synopsis, and to the Operations Manual, to ensure consistency with the changes below:

- Protocol Section 4.1, Overall Study Design and Plan, Figure 1. Study Schematic and Protocol Appendix D. Activity Schedule: Remove Weeks 64 and 76 as an on-site visit.
- Update to Appendix F, Operations Manual: Section 2.1, Individual Treatment Period Visit Activities and Section 2.2, Individual Post-Treatment Period Visit Activities (Week 64 and Week 76) to remove vital signs, EDSS, T25FW, 9HPT, urine drug and alcohol test, PK and ADA sample collections; Section 3.6 Scales and Questionnaires table to remove EDSS T25FW, 9HPT from Follow-up at Weeks 64 and 76.

Rationale:

By January 2021, all study subjects had completed 52 weeks of therapy. A recent, planned efficacy analysis revealed that elezanumab therapy provided no beneficial effects. A lack of efficacy was observed on all endpoints.

The study initially had scheduled in person site visits at Week 64 and Week 76. The purpose of these visits was to perform assessment of the primary endpoint to better understand the durability of improvement observed at Week 52. Because there were no beneficial drug effects at Week 52, there is no scientific purpose to having the subjects return for in person visits. The ongoing COVID-19 pandemic also provides a strong justification for NOT having subjects perform unneeded in person site visits.

The collection of safety-related information by phone every 4 weeks through Week 76, including AEs, C-SSRS assessments, and pregnancy testing results will continue.

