During the course of the study, MRI scans will be performed at three time points: at Screening (Baseline MRI), Week 24 and Week 52/Early Discontinuation. The screening MRI will be evaluated by the local radiologist and the radiologist's report reviewed by the investigator before Dose 1 at Week 0-Baseline visit to determine subject's eligibility. For the subjects enrolled in the study, the Screening MRI will

serve as the Baseline MRI for assessment of MRI outcome measures. The time window for MRI is \pm 7 days. MRI scans from all protocol-required time points will be evaluated by a local radiologist, and the local radiologist's reports will be reviewed by the site investigator for disease activity. Sites should use the same local radiologist to evaluate all the MRI collected through the entire duration of the study to the extent possible.

The MRI scans will include all or a subset of the following parameters:

- 3D T1 weighted
- T2 FLAIR
- MTR
- PD/T2
- T1 post Gadolinium
- DTI
- Spine STIR

For each study site, the MRI scanner, associated equipment and imaging parameters may not be changed during the length of the study without prior sponsor approval.

COVID-19 Pandemic-Related Acceptable Protocol Modifications

MRI assessments may be collected up to 12 weeks after the projected visit for the missed time points at Weeks 24 and 52 with the sponsor's consent due to reasons related to the COVID-19 pandemic. However, all MRI assessments projected to be obtained on or before mid-November 2020 must be completed by the end of November 2020.

To accommodate scheduling of the vast volume of projected Week 52 MRIs in December 2020, at the discretion of the sponsor, sites may schedule Week 52 MRIs up to -28 days of their projected Week 52 visit.

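### The ANCOVA listed for the exploratory cumulative total GAD and T2 lesion counts omits the baseline count, which can cost precision but adds no bias (low priority)

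*SAP*

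**What the plan says.** Protocol section 3.7 lists lesion counts among the MRI endpoints and leaves the detail to the SAP. SAP section 4.3.3 classes the cumulative lesion counts as exploratory, and section 4.6 makes no multiplicity adjustment.

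SAP section 9.4.11 names ANCOVA for four cumulative counts: total GAD, total T2, post-baseline GAD, and post-baseline new and enlarging T2. The only model description for them is: "The model for the analysis of the cumulative number of total lesions will include treatment, the stratification factors of diagnosis of MS", followed by background immunotherapy. It gives no covariate list for the two post-baseline counts.

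Two scan rules follow. The first reads: "For the cumulative number of lesions during the treatment period, only subjects with Baseline, Week 24, and Week 52 MRIs will be included". The second, which governs the post-baseline counts, asks for the two later scans and does not mention Baseline.

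The same section has a change-from-baseline list that includes a lesion count, "Change from Baseline in cervical spinal cord area, volume and number of lesions". The model for that list ends with "background MS immunotherapy (Yes or No), and the baseline value".

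Section 3.17 of the Operations Manual (Protocol Appendix F) says that the Screening MRI will "serve as the Baseline MRI for assessment of MRI outcome measures". The investigator reviews its report before the first dose.

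**The concern.** All three listed terms are categorical, so the ANCOVA as written has no continuous covariate. The obvious one, the subject's own pre-dose lesion count, is collected and cannot be affected by treatment. If the total includes the Baseline scan, part of the outcome is variation that existed before randomisation and that the model leaves in the residual.

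What is at stake is the width of the confidence interval for these two counts. That matters for a null result as well, since a narrower interval says more about which effects can be excluded.

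**Working it through.** **Plan's own figures.** The documents give no SD, correlation, standard error or power for any lesion count, so there is no figure to reproduce. The power statement in SAP section 4.4 is not tied to lesion counts and is unaffected.

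**Which scans are summed.** The treatment-period count needs Baseline, Week 24 and Week 52 scans; the post-baseline count needs only the last two. This points to Baseline being summed into the total. But the first rule speaks of the treatment period, not of the total, and no summation formula is given. Both readings are therefore carried below.

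**Assumptions.** Equal variance at each scan and a common between-scan correlation rho, within arm and strata. The SE ratio is the unadjusted SE divided by the baseline-adjusted SE, which is 1/sqrt(1 − r²). Here r² is the share of outcome variance explained by the baseline count.

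- Baseline summed (three scans): r² = (1 + 2 rho)/3, so the ratio is sqrt(3/(2(1 − rho))).
- Baseline not summed (Week 24 + Week 52): r² = 2 rho²/(1 + rho).

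| rho | r², summed | SE ratio, summed | r², not summed | SE ratio, not summed |
|---|---|---|---|---|
| 0 | 0.333 | 1.22 | 0 | 1.00 |
| 0.3 | 0.533 | 1.46 | 0.138 | 1.08 |
| 0.5 | 0.667 | 1.73 | 0.333 | 1.22 |
| 0.7 | 0.800 | 2.24 | 0.576 | 1.54 |
| 0.9 | 0.933 | 3.87 | 0.853 | 2.60 |

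**Equal variances.** At rho 0 with Baseline summed, let the baseline variance be v times that of a later scan. The ratio is then sqrt((v + 2)/2): 1.06 at v = 0.25, 1.12 at v = 0.5 and 1.41 at v = 2.

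**Skewed counts.** A simulation used 4,000 trials per scenario, three arms of 50, gamma-Poisson counts with a mean of 0.5 or 2 per scan, and two binary stratum terms. At between-scan correlations of 0.00, 0.40, 0.58 and 0.78:
- SE ratio for the three-scan total: 1.22, 1.62, 1.89 and 2.63.
- SE ratio for the post-baseline sum: 1.00, 1.16, 1.33 and 1.78.
- Type I error at nominal 5%: 4.7–5.6% for the unadjusted total and 4.2–5.3% for the adjusted total (Monte Carlo SE 0.34 points).
- With a true 40% post-baseline reduction, the true differences are 2 × 0.5 × 0.4 = 0.40 and 2 × 2 × 0.4 = 1.60 lesions. The unadjusted total returned −0.397, −0.402, −1.613 and −1.591, so the difference in means is not diluted.

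These are sparse, GAD-like counts. They do not represent T2 counts.

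**Overlap with the planned post-baseline GAD count.** Write the three-scan total as B + P, with B the Baseline count and P the Week 24 + Week 52 count. Once B is in the model, regressing B + P instead of P raises the coefficient of B by 1 and leaves the treatment coefficient unchanged. In the same subjects the two adjusted analyses therefore give the same treatment estimate.

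Without adjustment, the SE of the total relative to that of P is sqrt((3 + 6 rho)/(2 + 2 rho)). This is 1.22 at rho 0 and sqrt(6/3) = 1.41 at rho 0.5. At rho 0 the planned post-baseline GAD count already gives the whole gain. At rho 0.5 the 1.73 splits into 1.41 × 1.22: the first factor comes from analysing P, and only the 1.22 would remain, if the unstated model for P has no baseline term.

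**The case against.** The strongest case against is redundancy. A post-baseline GAD count is already planned and, once both are adjusted, it carries the same treatment estimate as the three-scan total. For T2, if a persisting lesion counts once and lesions do not resolve, the total is baseline plus new lesions, and adjusting it for baseline reproduces an adjusted new-lesion analysis. The plan already analyses new and enlarging T2 lesions. With exploratory endpoints and an efficacy analysis already reported, little would change.

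Most of this stands, and it limits the size of the gain. It does not remove the point: if Baseline is summed, the planned total-count contrasts still carry pre-dose variation. The T2 overlap is also inexact, because the planned count includes enlarging lesions and the SAP does not say how persisting lesions enter the total.

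Stronger readings that a reader might infer, and that the documents do not support:
- *The lesion comparison is biased or its type I error inflated.* Under randomisation, leaving out a pre-dose covariate does neither. The restriction to subjects with all required scans is a separate matter, which the covariate does not create.
- *The standard error must be too wide.* If Baseline is not summed and the scans are uncorrelated, the ratio is 1.00.
- *The large ratios measure what the plan loses.* They apply to one contrast; the related planned analyses recover part of the loss.
- *The post-baseline GAD model wrongly omits baseline.* The SAP lists no covariates for it either way.
- *The cervical cord lesion count shows that the SAP contradicts itself.* That count is a change-from-baseline endpoint with its own model. It shows that adjusting a lesion count is within the SAP's practice, and no more.

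**Conclusion.** The omission is real on the text, and the point holds as a modest matter of efficiency. If Baseline is summed, the planned SE for the total counts is about 1.22 times the adjusted one at rho 0 and 1.73 times at 0.5. If it is not summed, the ratios are 1.00 and 1.22. The size rests on assumed equal variances and correlations, and on which scans are summed, which the SAP leaves to inference. No T2-like scenario supports a specific figure for T2. The primary ORS analysis is not touched. Low priority.

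**What to change.** In SAP section 9.4.11:

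1. Add the matching baseline count (GAD for GAD, T2 for T2) as a covariate in the ANCOVA of the two total counts.
2. State that the adjusted three-scan GAD total and the adjusted Week 24 + Week 52 GAD count give the same treatment estimate in the same subjects, and do not present them as separate evidence.
3. If the model for the post-baseline counts is written out, baseline GAD can be included in the GAD model.
4. As a clarification, say which scans are summed and whether a persisting T2 lesion counts once or at every scan.

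Protocol Appendix E reports: "A recent, planned efficacy analysis revealed that elezanumab therapy provided no beneficial effects". An adjusted analysis added after that should be labelled supplementary.

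The cost is one covariate and one degree of freedom in each of two models. If the three-scan rule governs the totals, no subject with a usable baseline read is lost. Item 3 would drop any subject who has Week 24 and Week 52 scans but no usable baseline GAD read.

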- b. Baseline MRI must be performed before first dose. Non-scheduled MRIs after baseline will be performed at the discretion of the subject's treating physician or in the case of early subject discontinuation, if it has been more than 4 weeks since the subject's most recent MRI. For MRI procedures, the visit window is ± 7 days. Refer to Section 3.17, MRI, for COVID-19 pandemic-related modifications.

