- Subjects may begin receiving an immunomodulator that is recommended by their treating physician and is considered to provide the best balance of benefit versus risk. If the prescribed

medication is one that is allowed in the protocol's Inclusion Criterion #10, the subject can continue in the trial. If another immunomodulator is prescribed, they will not receive further infusions and should be discontinued from the study.

In the event of a clinical MS relapse, a supplemental AE eCRF form should be completed (See Appendix C, Relapse Questionnaire).

Adverse Events of Special Interest (AESI)

Infusion Reactions

The investigator or qualified designee will evaluate the infusion site area from Week 0 – Baseline through the end of the study. Any observation of infusion site reaction after the start of infusion must be recorded as an adverse event (AE).

Further information on monitoring of elezanumab infusion reactions is presented in Appendix D.

Collection of Data Regarding Known Complications of the Disease Under Study

Natural progression of MS (including new or worsening neurological symptoms and signs) is expected in the subjects. Disease progression will be assessed at pre-determined intervals throughout the treatment period by standardized criteria (such as the EDSS+, MSIS-29 version 2, MFIS, MSIOA) and recorded within the electronic Clinical Outcome Assessments (eCOA) for risk/benefit determinations. Therefore, "disease progression" or other similar verbatim terms related to disease status SHOULD NOT be recorded on the AE case report form (CRF) pages. Falls will not be recorded as AEs unless they lead to other injury or represent a change in frequency or character from pre-randomization falls.

Similarly, the slow progression of pre-existing disease-related signs and symptoms clearly associated with the disease during the treatment period will not be reported as AEs unless these signs and symptoms are judged by the investigator to have become unusually severe or accelerated, or if the investigator suspects the deterioration of disease-related signs and symptoms to be potentially related to the investigational drug. If there is any uncertainty about the worsening of an AE being due solely to the disease under the treatment protocol, it should be reported as an AE or SAE as appropriate.

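### Cumulative MRI lesion counts are analysed only in subjects with every scheduled scan, and the SAP does not say how an early-discontinuation MRI is counted

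*SAP*

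**What the plan says.** SAP 9.4.11 analyses the cumulative T1 GAD-enhancing and T2 lesion counts by ANCOVA. The model it states, for the total counts, has treatment and the two stratification factors. Two inclusion rules apply. For the treatment-period totals: "For the cumulative number of lesions during the treatment period, only subjects with Baseline, Week 24, and Week 52 MRIs will be included". For the post-baseline counts: "For the cumulative number of lesions post-baseline, only subjects with Week 24 and Week 52 will be included".

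SAP 9.1 says that all efficacy endpoints are analysed on the mITT set, and SAP 4.3.3 lists these counts among the exploratory efficacy endpoints. No reason is given for departing from mITT. The multiple imputation in SAP 9.3.1 covers EDSS, T25FW and 9HPT only, and no sensitivity analysis is named for MRI.

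Operations Manual 3.17 places the scans "at Screening (Baseline MRI), Week 24 and Week 52/Early Discontinuation". The visit notes in Operations Manual 2.1 call for an MRI "in the case of early subject discontinuation, if it has been more than 4 weeks since" the previous one. The SAP gives neither MRI visit windows nor a rule for assigning an ED scan to a visit.

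**The concern.** The rule makes this a completers-only comparison of disease activity, while the documents describe ways in which disease activity can end participation.

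- **Relapse treatment (Operations Manual 4.1).** After a relapse a subject may start a new immunomodulator. "If another immunomodulator is prescribed, they will not receive further infusions and should be discontinued from the study".
- **MRI findings (Operations Manual 3.19).** Subjects with treatment-emergent MRI findings are considered for stopping treatment if clinically indicated. The outcome being analysed can therefore contribute to a subject's exclusion from the analysis.
- **Progression (Operations Manual 4.1).** Disease progression is a recorded reason for discontinuation.

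At stake are the precision of the lesion comparison, its freedom from bias, and whether two programmers would handle the same ED scan in the same way.

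**Working it through.** **1. The plan's own figure.** The only planning calculation is in SAP 4.4, for the ORS: effect size 0.43, one-sided alpha 0.1, 80% power, 10% dropout.

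n per arm = 2(1.282 + 0.842)² / 0.43² = 48.8, rounded up to 49. Then 49 / 0.90 = 54.4, rounded up to 55, and 3 × 55 = 165. The figure reproduces. No calculation is given for lesion counts, so I take only the 10% dropout from it: 55 × 0.90 = 49.5 per arm.

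**2. Who is analysed under each reading of the ED scan.**

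| Subject | ED not taken as Week 52 | ED taken as Week 52 |
|---|---|---|
| Has Week 24 and Week 52 scans | in | in |
| Misses the Week 24 scan, has Week 52 | out | out |
| Has Week 24, stays in study, misses Week 52 | out | out |
| Has Week 24, stops, has an ED scan | out | in, with shorter follow-up and no time term |
| Stops before Week 24 | out | out |

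The last row is the same in both columns because one ED scan cannot fill both post-baseline visits.

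**3. Precision.** Suppose a proportion m of the non-dropouts misses each post-baseline scan, independently. The fraction analysed is f = 0.90 × (1 − m)², and the standard error rises by 1/√f − 1 relative to all 55 per arm. The documents give no value of m, so 5% to 20% is an assumption.

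| m | f | Analysed per arm | SE increase |
|---|---|---|---|
| 0 (dropout only) | 0.900 | 49.5 | 5% |
| 5% | 0.812 | 44.7 | 11% |
| 10% | 0.729 | 40.1 | 17% |
| 20% | 0.576 | 31.7 | 32% |

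These figures exclude all dropouts. Reading ED as Week 52 would recover some of them.

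**4. Bias within an arm.** Let a fraction d be excluded and have k times the lesions of those included (k is assumed). The included mean understates the arm's mean by 1 − 1/(1 + d(k − 1)).

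- d = 10%, k = 2, 3, 4: 9%, 17%, 23%.
- d = 20%, k = 2, 3, 4: 17%, 29%, 38%.
- k = 1: none.

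**5. Bias between arms.** All inputs here are assumed.

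- *Equal true means of 1, with 5% and 15% excluded.* The included means are 1/(1 + 0.05(k − 1)) and 1/(1 + 0.15(k − 1)). For k = 2 they are 0.952 and 0.870. For k = 3 they are 0.909 and 0.769. For k = 4 they are 0.870 and 0.690. The spurious difference is 0.08 to 0.18 of the true mean, and swapping the exclusion rates flips its sign.
- *Equal included means of 1.0, k = 3, with 5% and 15% excluded.* The true means are 0.95 + 0.05 × 3 = 1.10 and 0.85 + 0.15 × 3 = 1.30. A true ratio of 1.30/1.10 = 1.18 is hidden.
- *Equal exclusion and equal k, no true effect.* The comparison is unbiased.

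With the same k above 1 in both arms, the arm that loses more subjects looks better than it should. Whether that moves the result toward or away from no difference depends on which arm it is and on the true effect.

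**The case against.** The other side has good points.

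- **Comparability.** Requiring the same scans from everyone is a prespecified way to make a cumulative sum comparable. It is defensible where scans are missing for reasons unrelated to lesions.
- **The ED scan may be used.** A reader might infer that it is never used. The documents do not show that. The Operations Manual pairs it with Week 52, and the SAP is silent rather than excluding. The active-lesion proportions and the change-from-baseline models carry no complete-scan rule. The T1 GAD table is by visit ("The number of T1 GAD-enhancing lesions at each visit (Baseline, Week 24, Week 52) will be summarized categorically"), which again leaves the ED assignment open. The scan also has a safety use, through local radiology review and the MRI safety evaluation in Protocol 3.4.
- **The link to disease activity is limited.** A reader might infer that the subjects with the most active disease are the ones removed, or that the result is pulled toward no difference. Neither is established. Relapsing subjects may stay in the study untreated, on steroids, or on a permitted immunomodulator. Protocol 4.2 chooses a population at reduced relapse risk. The MRI-findings clause concerns treatment and is discretionary. No document gives lesion rates in those who leave.
- **Most of the precision loss is assumed.** Beyond 5%, it comes from m. Operations Manual 3.17 softens pandemic misses by allowing scans up to 12 weeks late and, at the sponsor's discretion, Week 52 scans up to 28 days early.
- **Missing at random.** SAP 4.7 makes that assumption for pandemic-related gaps.

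The last point does not rescue the analysis. The assumption is conditional on observed data, but this ANCOVA discards the observed Week 24 count of anyone without a Week 52 scan. A complete-case estimate can be biased even when the assumption holds. The other points narrow the claim without removing the complete-case rule or the missing ED rule.

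**Conclusion.** The point holds as a cheap improvement to exploratory analyses. What the documents establish is a complete-case rule that departs from mITT without explanation, no assignment rule for ED scans, no time adjustment if they count as Week 52, and no MRI sensitivity analysis.

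The 5% loss of precision rests on the SAP's own dropout figure. The 11% to 32% range rests on an assumed miss rate. Bias is possible because discontinuation can follow MRI findings, relapse treatment or progression, but its size and direction cannot be fixed from the documents. The primary endpoint and the sample size are untouched.

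**What to change.** In SAP 9.4.11, for the post-baseline GAD-enhancing and new/enlarging T2 counts:

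1. Include every mITT subject with a baseline and at least one post-baseline MRI, counting ED scans where they were obtained. State how an ED scan is assigned to a visit in the other MRI summaries.
2. Analyse by negative binomial regression with treatment and the two stratification factors. Use an offset of log(number of post-baseline scans) for GAD-enhancing lesions and log(time from baseline scan to last scan) for new/enlarging T2 lesions.
3. Where the Week 24 scan is missing, use the Week 52 T2 count only if the central reading already gives it against baseline.
4. Keep the complete-scan ANCOVA as a sensitivity analysis, and report exclusions by arm and reason.

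The cost is SAP wording and a little programming, and no new scans are needed. The result becomes a rate ratio instead of a difference in means. Recovery will be partial: the ED MRI is conditional on the 4-week interval, is not needed at a virtual ED visit, and cannot help a subject with no post-baseline scan.
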